## **18.5 Handling Missing or Incomplete Dates/Times**

### **18.5.1 IMP Start and Stop Dates**

In evaluation of valid efficacy and safety assessments (assessment is considered valid if assessment date-date of last IMP  $\leq 7$  days), a missing date of last IMP will be imputed by the latest attended Visit in the study before the safety follow-up.

Exposure with missing IMP start or stop date will not be calculated.

### **18.5.2 Withdrawal Date**

For withdrawn patients with a missing Withdrawal Visit, the date of the last attended visit will be used in the calculation of time to withdrawal from study.

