8.4 Withdrawal Visit

Patients who withdraw from the study prior to the Completion Visit will be asked to attend a Withdrawal Visit, if at all possible. The visit must be scheduled as soon as possible after withdrawal.

No new information will be collected from patients who withdraw, except information collected in relation to the scheduled Withdrawal Visit or needed for the follow-up of adverse events (section 10.5).

The reason for withdrawal must be recorded on the *Reason for Withdrawal Form*.

For a patient and/or his or her legal representative (if applicable) who withdraw assent/consent:

- if the patient and/or his or her legal representative (if applicable) withdraw assent/consent during a visit and then agrees to it being the final visit, the investigator will complete the visit as a Withdrawal Visit and all the data collected up to and including this visit will be used
- if the patient and/or his or her legal representative (if applicable) withdraw assent/consent during a telephone conversation, the investigator will ask the patient if he or she will attend a Withdrawal Visit. If the patient:
 - agrees to attend a Withdrawal Visit, all the data collected up to and including this visit will be used
 - refuses to attend a Withdrawal Visit, the investigator should attempt to follow the patient's safety and future treatment; any information collected will only be recorded in the patient's medical record

- if the patient and/or his or her legal representative (if applicable) explicitly request that his or her data collected from the time of withdrawal of assent/consent onwards not be used, this will be respected

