17.4 Patient Disposition

Patient disposition will be summarised and include the number of patients who completed and the number of patients who withdrew from treatment, as well as the number of patients in each analysis set (APTS and FAS).

The number of patients who withdrew from treatment will be summarised by primary reason for withdrawal as well as by all reasons for withdrawal.

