### 6.2 Withdrawals

The number of patients who withdrew will be summarized for all patients, by lead-in studies and by lead-in treatment, respectively, and by primary reason for withdrawal and all reasons for withdrawal.

Patients who withdrew will be listed and the listing will include the number of days in the study until withdrawal, the number of days on IMP, the primary reason for withdrawal and all reasons for withdrawal.

Kaplan-Meier plots of time to withdrawal will be presented for all patients, by lead-in studies and by lead-in treatment, respectively. The time will be calculated from the date of first dose of IMP in the current trial to the date of completion or withdrawal. Patients who completed study will be regarded as censored.

All tables, graphs, and listings will be based on the APTS.

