## 9 Exposure and Compliance

Exposure (days) to IMP will be calculated as:

- Date of last dose of IMP – Date of first dose of IMP in study 12712A + 1

Exposure to IMP will be summarized for all patients and by lead-in study and by lead-in treatment using descriptive statistics, and, will include the patient years of exposure (PYE). PYE will be calculated as the sum of the number of days of exposure to IMP for each patient, divided by 365.25 days.

In addition, exposure to IMP will be categorized in intervals (1 – 14 days, 15 – 35 days, 36 – 70 days, 71 – 105 days, 106 – 140 days, 141 – 182 days and >182 – days) and summarized by lead-in study and by lead-in treatment. Missing values of exposure will not be imputed.

Non-compliant days are days on which no IMP has been taken, less than the full dose of IMP has been taken, or more than the full dose of IMP has been taken.

Compliance (%) with IMP will be calculated as:

- $(\text{date of Completion/Withdrawal Visit} - \text{date of Visit 1} - \text{number of days of non-compliance}) / (\text{date of Completion/Withdrawal Visit} - \text{date of Visit 1}) \times 100\%$

where the number of non-compliant days is defined as the sum of all non-compliant days in the treatment period.

Compliance with IMP will be categorized as “≤80% compliant” or “>80% compliant”. The number and percentage of patients in each category will be summarized by lead-in study and lead-in treatment, respectively, by visit interval and for the entire study.

The mean and modal dose of IMP will be calculated for each patient and summarised (mean, median, and lower and upper quartiles for the mean and counts for the modal dose). IMP dose level at the completion or withdrawal of the study will be summarized. Number and percentage of patients who reached highest and lowest dose level will be summarised. In addition, number and percentage of patients with each dose level will be summarised by visit.

Number of patients who exposed to oral drops will be summarized.

Exposure and compliance will be summarized based on the APTS.

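### When there is no Withdrawal Visit, SAP 18.5.2 dates the withdrawal at the last attended visit even if a later dose is on record: a minor timing error with a simple repair

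*SAP*

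**What the plan says.** SAP 6.2 plans Kaplan-Meier plots of time to withdrawal for all patients, by lead-in study and by lead-in treatment. "The time will be calculated from the date of first dose of IMP in the current trial to the date of completion or withdrawal". The withdrawal date is not defined further there. On censoring: "Patients who completed study will be regarded as censored". The same section plans a listing of withdrawn patients that shows days in study next to days on IMP.

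SAP 18.5.2, one of the rules for missing or incomplete dates, adds: "For withdrawn patients with a missing Withdrawal Visit, the date of the last attended visit will be used". The rule applies when time to study withdrawal is derived. This implies, without saying so, that the Withdrawal Visit date is used when that visit took place.

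SAP 9 defines exposure as "Date of last dose of IMP – Date of first dose of IMP in study 12712A + 1". SAP 18.5.1 leaves exposure uncalculated when the first or last dose date is missing. For judging whether an assessment is valid, SAP 18.5.1 replaces a missing last-dose date with the latest attended visit and excludes the safety follow-up. SAP 18.5.2 has no such exclusion, and it does not say whether a telephone contact is an attended visit.

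**The concern.** A patient who took a dose on a known date had not stopped treatment before that date. The fallback ignores this. It places the withdrawal at the last attended visit even when the database holds a later dose. Three things follow.

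- Withdrawals without a Withdrawal Visit collect at visit weeks and appear earlier than they were.
- The listing can print a row with more days on drug than days in study.
- A treated patient with no visit after Visit 1 can receive a time of zero or less, which is not a usable survival time.

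With the relapse and loss-of-remission analyses removed (SAP 17), this is the only Kaplan-Meier output still planned. Because 18.5.2 does not say which contacts count, two programmers could also draw different curves from the same data.

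**Working it through.** **Inputs from the documents.** Treatment-period contacts are at Weeks 0, 1, 2, 3, 4, 6, 8, 10, 12, 15, 18, 22 and 26 (SAP Appendix II). Visits 4, 6, 8, 10 and 12, at Weeks 3, 6, 10, 15 and 22, are by telephone (Protocol 8.3). Site visits are therefore at Weeks 0, 1, 2, 4, 8, 12, 18 and 26. The safety follow-up is about 30 days after last dose (Protocol 8.5).

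**Assumptions, not in the documents.** Withdrawals are spread evenly over 26 weeks, and visits fall on their nominal days. Between 15% and 30% of patients withdraw, and 10% to 100% of withdrawers have no Withdrawal Visit. The days-in-study column is taken to use the same time as the plot, since the SAP gives no other formula. The planned size (about 850; 1200 × 0.85 × 0.85 = 867, or 1200 × 0.80 × 0.85 = 816) does not affect results expressed in points.

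**Individual rows.** Day 0 is Visit 1 and, unless stated otherwise, the first dose.

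- Seen at Week 18 (day 126), last dose on day 146, no Withdrawal Visit. Days in study = 126 - 0 = 126. Days on IMP = 146 - 0 + 1 = 147. The next contact is Week 22, so it makes no difference whether telephone contacts count.
- All contacts kept through Week 22, last dose on day 181, no Withdrawal Visit. Days on IMP = 182. Days in study = 154 if the Week 22 call counts (28 fewer), or 126 if only site visits count (56 fewer). These are the largest nominal gaps.
- Withdrawal Visit on the last-dose day, for example day 100. Days in study = 100 and days on IMP = 101, because SAP 6.2 has no +1.
- No visit after Visit 1. Days in study = Visit 1 date - first-dose date = 0, or -1 if dosing starts the next day. That is plausible, since Protocol 6.1 prefers morning dosing.

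**Mean backdating of an imputed withdrawal** = sum of squared gaps / (2 × 26), in weeks.

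- All contacts: gaps 1, 1, 1, 1, 2, 2, 2, 2, 3, 3, 4, 4. Sum of squares 70; 70/52 = 1.35 weeks = 9.4 days.
- Site visits only: gaps 1, 1, 2, 4, 4, 6, 8. Sum of squares 138; 138/52 = 2.65 weeks = 18.6 days.

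A simulation in whole days (300 runs per scenario, n = 850) gave about 9 and 18 days.

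**Effect on the curve at Week 18** = withdrawal rate × share imputed × (gap to next contact / 26). The gap is 4 weeks for all contacts and 8 weeks for site visits only. Each entry is the drop in points, with the simulated value in brackets.

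| Withdrawal rate | Share imputed | All contacts | Site visits only |
|---|---|---|---|
| 15% | 10% | 0.23 (0.21) | 0.46 (0.45) |
| 20% | 30% | 0.92 (0.91) | 1.85 (1.84) |
| 20% | 50% | 1.54 (1.49) | 3.08 (3.11) |
| 30% | 100% | 4.62 (4.48) | 9.23 (9.14) |

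**Away from the visit step.** With 20% withdrawal and 30% imputed, the simulated difference one week before the next visit is about 0.2 points. Averaged over 26 weeks it is 0.06 × 9.4/182 = 0.3 points, or 0.06 × 18.6/182 = 0.6 points. On the day before Week 26 it is 0.0 in every scenario, because every withdrawal is still counted as an event.

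**The case against.** The best defence is that 18.5.2 is a declared fallback for a missing date, and that exposure and time in study are different quantities which may end on different days. That is correct. A reader might infer that SAP 6.2 and 18.5.2 contradict each other; they do not.

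A reader might also infer that the curve mixes events dated too late with events dated too early, since Protocol 8.4 says of the Withdrawal Visit: "The visit must be scheduled as soon as possible after withdrawal". But the same section lets a visit at which consent is withdrawn serve as the Withdrawal Visit, with no lag. The documents give nothing from which to size a lag. Only the early side can be shown.

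The larger figures are easy to overread. Week 18 is a visit step, where the difference peaks. The site-visits-only results rest on the less natural reading, because the protocol numbers telephone contacts as visits (8.3) and says that visits may take place in clinic or by phone (4.1). Direction is not fully settled either. If the safety follow-up counted as the last attended visit, the date would move later, to about 30 days after last dose.

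The plot is a disposition display. No primary or secondary endpoint uses it, no test compares the curves, and the documents give no reason why Withdrawal Visit attendance should differ by lead-in treatment.

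Finally, the last-dose date will not always exist. If consent is withdrawn by telephone and the visit is refused, later information goes only to the medical record (Protocol 8.4). Exposure is then not calculated, and no conflicting row appears.

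All of this limits the point without removing it. Where the last-dose date is recorded and later than the last visit, the rule still gives a date the database shows to be too early, and nothing prevents a time of 0 or -1.

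**Conclusion.** The concern holds as a minor defect in date handling. It affects only the timing of withdrawals without a Withdrawal Visit. With even withdrawal, these move earlier by about 9 days on average (telephone contacts counted) or about 18 days (site visits only), with a nominal maximum of 4 or 8 weeks. At Week 18 the curve is 0.9 or 1.8 points low with 20% withdrawal and 30% imputed. The scenarios tried run from about 0.2 to 9 points, and the documents give neither rate. The effect falls close to zero just before the next visit, and the final retention level does not change. A reader who infers that overall retention is biased goes further than the plan's text allows.

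Nor do the documents require the clock to end at last dose for everyone. Protocol 17.4 does count "the number of patients who withdrew from treatment", but SAP 6.1 and 18.5.2 speak of withdrawal from study. Ending at last dose throughout would replace that quantity with treatment discontinuation.

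**What to change.** Keep time to withdrawal from study as the quantity, and make two edits.

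- **SAP 18.5.2:** when the Withdrawal Visit is missing, use the later of the recorded last IMP dose date and the last attended treatment-period contact. State that telephone contacts count and that the safety follow-up is excluded, as in SAP 18.5.1.
- **SAP 6.2:** add 1 day to match SAP 9, with a minimum of day 1. State that the days-in-study column of the listing uses the same derivation.

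In the first example above, days in study becomes 146 - 0 + 1 = 147, equal to days on IMP. The patient with no visit after Visit 1 gets at least day 1.

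The cost is a sentence or two and a changed derivation, with no new data collection. The limitation is that patients with no recorded last-dose date still fall back to the last contact, so some backdating remains.

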### **18.5.3 Medication Start and Stop Dates**

In order to assign all medications to an analysis start-and stop phase, missing or incomplete start-or stop dates will be imputed. Ongoing medications at the end of a study will not be assigned a stop phase in that study.

No duration will be calculated for medications with imputed start-or stop date, or for ongoing medications.

For further details, see [Data Handling Plan](#).

### **18.5.4 Adverse Event Start and Stop Dates**

Incomplete adverse start dates will be imputed before handling of incomplete dates for change in intensity or seriousness.

For further details, see [Data Handling Plan](#).

## **Appendix II**

### **Study Flow Chart**

## Study Flow Chart

**Table 1 Study procedures and Assessments**

Visit	Base-line Extension A	Treatment Period												Completion /With-drawal a	Safety Follow-up b
Visit Number	1	2	3	4 c	5	6 c	7	8 c	9	10 c	11	12 c	13	14	
End of Week	0	1	2	3	4	6	8	10	12	15	18	22	26	30	
Visit Window d (days relative to nominal visit)	0 2	± 2	± 2	± 2	± 2	± 2	± 2	± 2	± 2	± 2	± 5	± 5	± 5	± 5	
Baseline Extension A Procedures and Assessments															
Signed informed consent/assent	✓														
Inclusion/exclusion criteria	✓														
Efficacy Assessments															
CDRS-R	✓ e	✓	✓		✓		✓		✓		✓		✓		
CGI-S	✓ e	✓	✓		✓		✓		✓		✓		✓		
CGI-I f	✓ e	✓	✓		✓		✓		✓		✓		✓		
BRIEF (7-11 years at Baseline Extension A)	✓				✓		✓		✓		✓		✓		
BRIEF-SR (12-18 years at Baseline Extension A)	✓				✓		✓		✓		✓		✓		
CGAS	✓ e				✓		✓		✓		✓		✓		
PedsQL VAS (PRO)	✓ e				✓		✓		✓		✓		✓		
Vortioxetine Quantification															
Blood sampling vortioxetine quantification	✓ e				✓								✓		
Safety Assessments															
Adverse events	✓ g	✓	✓	✓	✓	✓	✓	✓	✓	✓	✓	✓	✓	✓ h	
Blood and urine sampling for clinical safety laboratory tests	✓ e,i				✓								✓		
Vital signs	✓ e	✓	✓		✓		✓		✓		✓		✓		
Weight and height	✓ e								✓				✓		
Menstrual cycle and Tanner score	✓								✓				✓		
ECGs	✓ e				✓								✓		
Examinations	✓ e							✓					✓		

Visit	Base-line Extension A	Treatment Period												Completion /Withdrawal a	Safety Follow-up b
		2	3	4 c	5	6 c	7	8 c	9	10 c	11	12 c			
Visit Number	1	2	3	4 c	5	6 c	7	8 c	9	10 c	11	12 c	13	14	
End of Week	0	1	2	3	4	6	8	10	12	15	18	22	26	30	
Visit Window d (days relative to nominal visit)	0	± 2	± 2	± 2	± 2	± 2	± 2	± 2	± 2	± 2	± 5	± 5	± 5	± 5	
(physical and neurological)															
PAERS	✓ e	✓	✓	✓	✓	✓	✓	✓	✓	✓	✓	✓	✓		
C-SSRS	✓ e	✓	✓	✓	✓	✓	✓	✓	✓	✓	✓	✓	✓		
Other Study Procedures															
IMP dispensed	✓	✓	✓		✓		✓		✓		✓		✓		
Possible change in IMP dose		✓	✓		✓		✓		✓		✓		✓		
IMP returned and IMP accountability		✓	✓		✓		✓		✓		✓		✓		
Recent and concomitant medication	✓ g	✓	✓	✓	✓	✓	✓	✓	✓	✓	✓	✓	✓		
Pregnancy test j	✓ e				✓								✓		
Drug and alcohol screen e,k															

a This visit should take place as soon as possible after the patient withdraws from the study.

b This can be a telephone contact, unless an SAE has occurred since the last visit or unless there was a clinically significant abnormal safety laboratory test value at the last visit. In such cases, safety follow-up(s) must be scheduled to allow for a medical examination and/or blood/urine sampling. Further safety follow-up visits beyond 30 days may be needed as judged by the investigator (if further safety follow-up visits are performed, these must be recorded in the patient's medical record, and not in the eCRF).

c A telephone contact. The patient and/or legal representative and/or the investigator can request an unscheduled site visit to discuss their current dose. During such an unscheduled site visit, the CDRS-R, CGI-S, CGI-I, PAERS and C-SSRS must be performed.

d If the date of a patient visit does not conform to the study plan, subsequent visits should be planned to maintain the visit schedule relative to Baseline Extension A. The number of days between 2 visits must not exceed the number of days for which IMP is provided for in the drug kit.

e Values from assessments and procedures conducted at Visit 12 (Completion Visit) of Study 12709A or 12710A will be the Baseline Extension A Visit values for this study (12712A).

f The assessment of the CGI-I should be in reference to Baseline A in the lead-in studies.

g Ongoing adverse events and concomitant medications (at Completion Visit 12 in Study 12709A or 12710A) will be transcribed to the eCRF Adverse Event Form and Concomitant Medication Form.

h Only for adverse events ongoing at Completion/Withdrawal and new SAEs.

i The 12712A Hormones panel is to be collected using a separate study-specific kit

j Females >10 years of age or female patients at lower age judged by the investigator to be of childbearing potential. Additional pregnancy tests during the study will be performed according to local requirements.

Females <11 years will be tested using a urine hCG test and females >11 years will be tested using a blood hCG test.

- k It is not mandatory to screen for drugs and/or alcohol. However, it can be performed at any visit, at the discretion of the investigator.

## **Appendix III**

### **SAS® Code**

## SAS® Code

### MMRM for analysing continuous endpoints

```
proc mixed noclprint data=xyz ic method=reml;  
  class usubjid country week lead-in _study;  
  model y=baseline country week lead-in_study*week baseline*week / s ddfm=kr;  
  repeated week/subject=usubjid type=un;  
  run;
```

## **Appendix IV**

### **PCS Criteria**

## PCS Criteria

**Table 2 Lundbeck PCS Criteria for Clinical Safety Laboratory Tests**

Laboratory Test	CDISC Term	Unit	PCS LOW	PCS HIGH
Haematology / Coagulation				
B-haemoglobin	HGB	g/dL	≤ 9.5 (women); ≤ 11.5 (men)	≥ 16.5 (women); ≥ 18.5 (men)
B-erythrocytes (red cell count)	RBC	x 10E12/L	≤ 3.5 (women); ≤ 3.8 (men)	≥ 6.0 (women); ≥ 7.0 (men)
B-haematocrit (packed cell volume)	HCT	V/V	≤ 0.32 (women); ≤ 0.37 (men)	≥ 0.50 (women); ≥ 0.55 (men)
B-MCV (mean cell volume)	MCV	fL	≤ 0.8 x LLN	≥ 1.2 x ULN
B-total leucocyte (white cell count)	WBC	x 10E9/L	≤ 2.8	≥ 16
B-neutrophils/leucocytes	NEUTLE	%	≤ 20	≥ 85
B-eosinophils/leucocytes	EOSLE	%		≥ 10
B-basophils/leucocytes	BASOLE	%		≥ 10
B-lymphocytes/leucocytes	LYMLE	%	≤ 10	≥ 75
B-monocytes/leucocytes	MONOLE	%		≥ 15
B-thrombocytes (platelet count)	PLAT	x 10E9/L	≤ 75	≥ 600
P-INR (prothrombin ratio)	INR	Ratio		≥ 2.0
B-prothrombin time	PT	Sec		≥ 18
Liver				
S-aspartate aminotransferase	AST	IU/L		≥ 3 × ULN
S-alanine aminotransferase	ALT	IU/L		≥ 3 × ULN
S-bilirubin	BILI	µmol/L		≥ 34
S-bilirubin, direct	BILDIR	µmol/L		≥ 12
S-bilirubin, indirect	BILIND	µmol/L		≥ 22
S-alkaline phosphatase	ALP	IU/L		≥ 3 × ULN
S-gamma glutamyl transferase	GGT	IU/L		≥ 200
S-alpha-glutathione S-transferase (alpha-GST)	GSTAL	µg/L		≥ 20
Kidney				
S-creatinine	CREAT	µmol/L		≥ 1.5 x ULN
B-urea nitrogen (BUN)	BUN	mmol/L		≥ 11
S-uric acid (urate)	URATE	µmol/L		≥ 510 (women); ≥ 630 (men)
Electrolytes				
S-sodium (natrum)	SODIUM	mmol/L	≤ 125	≥ 155
S-potassium (kalium)	K	mmol/L	≤ 3.0	≥ 6.0
S-calcium	CA	mmol/L	≤ 1.8	≥ 3.0
S-chloride	CL MG	mmol/L	≤ 90	≥ 117
S-magnesium	PHOS	mmol/L	≤ 0.6	≥ 1.3
S-phosphate (phosphorus, (inorganic)	BICARB	mmol/L	≤ 0.65	≥ 1.95
S-bicarbonate		mmol/L	≤ 12	≥ 38

Endocrine / Metabolic				
B-glucose, non-fasting/unknown	GLUC	mmol/L	≤ 3.4	≥ 9.4
B-glucose, fasting	GLUC	mmol/L	≤ 3.0	≥ 6.0
S-glucose, non-fasting/unknown	GLUC	mmol/L	≤ 3.9	≥ 11.1
S-glucose, fasting	GLUC	mmol/L	≤ 3.5	≥ 7.0
B-glycosylated haemoglobin, fasting	HBA1C	%		≥ 6.5
S-prolactin	PROLCTN	mIU/L		≥ 1350
S-thyrotropin/TSH	TSH	mIU/L	≤ 0.3	≥ 5.5
S-protein (total)	PROT	g/L	≤ 45	≥ 95
S-albumin	ALB	g/L	≤ 27	
Lipids				
S-cholesterol total, non-fasting/unknown	CHOL	mmol/L		≥ 7.8
S-cholesterol total, fasting	CHOL	mmol/L		≥ 6.2
S-triglycerides, non-fasting/unknown	TRIG	mmol/L		≥ 5.65
S-triglycerides, fasting	TRIG	mmol/L		≥ 4.2
S-LDL cholesterol, non-fasting/unknown	LDL	mmol/L		≥ 5.3
S-LDL cholesterol, fasting	LDL	mmol/L		≥ 4.9
S-HDL cholesterol, non-fasting/unknown	HDL	mmol/L	≤ 0.8	
S-HDL cholesterol, fasting	HDL	mmol/L	≤ 0.9	
Cardiac / Skeletal/Muscle				
S-creatinine kinase (total)	CK	IU/L		≥ 400 (women); ≥ 750 (men)
S-creatinine kinase MB isoenzyme	CKMB	µg/L		≥ 8.5 or
	CKMBCK	%		≥ 3.5% of total CK
S-lactate dehydrogenase (total)	LDH	IU/L		≥ 750
S-troponin I	TROPONI	µg/L		≥ 1.5
S-troponin T	TROPONT	µg/L		≥ 0.4
Infection				
S-C-reactive protein	CRP	mg/L		≥ 25
S-globulin (total)	GLOBUL	g/L	≤ 15	≥ 55
Urine				
Urinary pH	PH		≤ 4	≥ 9

S=serum; B=whole blood; U=urine

**Table 3 Lundbeck PCS Criteria for ECG Parameters**

ECG Parameter	CDISC Term	Unit	PCS LOW	PCS HIGH
Absolute Time Interval				
PR interval	PRMEAN	Msec		≥ 260
QRS interval	QRSDUR	Msec		≥ 150
QT interval	QTMEAN	Msec		≥ 500
Derived Time Interval				
Heart rate	HRMEAN	beats/min	< 50 and decrease ≥ 15	≥ 120 and increase ≥ 15
QTcB interval	QTCB	Msec	< 300	> 500 or increase > 60
QTcF interval	QTCF	Msec	< 300	> 500 or increase > 60
RR interval	RR	Mses	< 500	> 1200

Increase/decrease is relative to the baseline value

**Table 4 PCS Criteria for Vital Signs, Weight/BMI, and Waist Circumference**

Parameter	CDISC Term	Unit	PCS LOW	PCS HIGH
Waist circumference	WSTCIR	Cm	decrease $\geq$ 7%	increase $\geq$ 7%
Weight	WEIGHT	Kg	decrease $\geq$ 7%	increase $\geq$ 7%
Body Mass Index	BMI	kg/m 	decrease $\geq$ 7%	increase $\geq$ 7%
Pulse rate, supine/sitting/unknown	PULSE	beats/min	< 50 and decrease $\geq$ 15 $\geq$ 15	$\geq$ 120 and increase $\geq$ 15
Diastolic blood pressure, supine/sitting/unknown	DIABP	mmHg	$\leq$ 50 and decrease $\geq$ 15	$\geq$ 105 and increase $\geq$ 15
Systolic blood pressure, supine/sitting/unknown	SYSBP	mmHg	$\leq$ 90 and decrease $\geq$ 20	$\geq$ 180 and increase $\geq$ 20
Orthostatic systolic blood pressure a	OBP	mmHg	$\leq$ -30	
Orthostatic pulse rate a	OPR	beats/min		$\geq$ 20
Temperature b	TEMP	°C	decrease $\geq$ 2	$\geq$ 38.3 and increase $\geq$ 2

Increase/decrease is relative to the baseline value

aFor definition of orthostatic blood pressure and pulse rate, see text after Table 3

bNote, the diurnal variation may affect the temperature. Morning temperature is lower

